### **9.3 Sample Size/Power Calculations**

There is little preliminary data on the expected differences in the primary outcomes in previously drug-naïve patients following a washout. Several unpublished analyses provided ranges of possible differences between treated and placebo patients, as well as expected correlations between baseline and follow up measures. Therefore, sample size was based on a minimum effect size (i.e., absolute difference between any two groups divided by the standard deviation (SD)) using a two-sided significance level of  $\alpha=0.05$ , and a conservative correlation of 0.57 between baseline and follow up measures. A sample size of 56 per arm (224 total) at the end of the washout provides  $\geq 80\%$  power to detect a minimum effect size of 0.60 between any two treatment groups in either of the primary outcome measurements (see Table 3) for the closed-testing procedure as described above using a baseline-adjusted analysis of covariance. A higher effect size will result in significantly increased power. A total of 255 participants will be recruited to allow for a 10% loss to follow-up over the course of the study.

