**CONFIDENTIAL**

## ***9.1 Primary Outcome and Analyses***

Two primary outcomes each measuring  $\beta$ -cell function after 3-months of washout will be assessed for this trial. In order to maintain a study-wide  $\alpha=0.05$ , a closed testing procedure will be used to assess the primary outcome [89]. The closed testing procedure is a method of hierarchical testing which tests higher-order comparisons before allowing lower-level comparisons, thus controlling the type I error and preserving power. First,  $\beta$ -cell function will be compared across the four treatment groups using an analysis of covariance model adjusted for baseline  $\beta$ -cell function. From this model, the overall test of equality across the four treatment groups will be computed. If that overall test is significant at the  $\alpha=0.05$  level, then each of the four possible sets of three interventions will be compared in four separate analysis of covariance models. The final significance testing of any set of two treatment groups is only undertaken if the p-values for each of the two 3-intervention tests which include a particular two intervention group are both  $p<0.05$ . For example, for interventions  $I_1$ ,  $I_2$ ,  $I_3$  and  $I_4$ , the first analysis of variance test  $I_{1234}$  assesses whether there are any differences among the four groups. If the overall test across the four groups is not significant, testing concludes and no treatment group is declared different from any other. Alternately, if that initial 4-group test is significant at the  $\alpha=0.05$  level, four separate analysis of covariance models with combinations  $I_{123}$ ,  $I_{124}$ ,  $I_{134}$  and  $I_{234}$  are tested. The comparison  $I_{12}$  is only tested if both  $I_{123}$  and  $I_{124}$  are significant at  $p<0.05$  and so forth. The closed testing procedure is chosen as the primary outcome analysis to maintain an overall study-wide  $\alpha=0.05$  while preserving power and allowing each set of interventions to be compared under pre-specified circumstances. The two primary outcomes will be analyzed separately with a total type I error probability of 0.05 for each, i.e. without an adjustment for two separate outcomes.

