Each ANCOVA model will employ White's robust (information sandwich) estimate of the covariance matrix of the model coefficients as the basis for inference [90]. This approach preserves power and protects the type 1 error probability when the homoscedastic normal errors assumptions are violated.

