**Table 3: Power for a sample size of 224 at end of study (56/treatment arm)**

Minimum Power	Adjusted Effect Size	Correlation
84%	0.62	0.60
81%	0.60	0.57
77%	0.57	0.50

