release at Month 15 vs. treatment arm (adjusted for baseline), where the two models are fit simultaneously using Seemingly Unrelated Regression techniques¹⁻⁵. This provides an estimate of the treatment group difference in insulin sensitivity as well as the treatment group difference in the release of the beta-cell peptides, while allowing for the correlation among the insulin sensitivity and peptide release measures. This yields an estimate of the joint covariance structure of the two models, and allows a joint statistical test of both variables using a 2-DF chi-square test of the treatment arm difference in each model. Thus, we will be able to test whether both the insulin sensitivity and C-peptide (and insulin) release variables are different across treatment groups at Month 15, adjusted for their baseline value.

This approach will provide a clear answer to the question of whether the Month 15 result differs by treatment, adjusting for baseline measures. However, given that an underlying reciprocal relationship is expected, it is possible that a significant difference could be found between groups, but that this represents a proportional shift without a specific improvement in peptide release adjusted for sensitivity. In other words, the data points could lie on a different part of a shared relationship curve such that the change represents a mutually compensated change in these terms without a separate underlying change in beta-cell function. Therefore, if the results of the two model analysis are significant, further analysis will evaluate the patterns of change in either or both variables within each group.

Below is sample Primary Outcome R code for this primary analysis.

R code and sample output for primary outcome with Seemingly Unrelated Regression model using systemfit

```
> fit12=systemfit(list(Eq1 = log_mi ~ Treatment + log_mi_base,
  Eq2 = log_cpeptide_steady ~ Treatment +
  log_cpeptide_steady_base),
  method='SUR',
  data=RISEM15)

> linearHypothesis(fit12,test = "Chisq",
  c('Eq1_TreatmentTreat2=0','Eq2_TreatmentTreat2=0'))

Hypothesis: Eq1_TreatmentTreat2 = 0      Eq2_TreatmentTreat2 = 0

Model 1: restricted model
Model 2: fit12

  Res.Df   Df   Chisq     Pr(>Chisq)
1    xxx
2  xxx-2   2   xxxx   x.xxx ← pvalue for the 2-DF joint statistical test
of both sensitivity and secretion variables of the treatment arm
difference
```

References:

1. https://en.wikipedia.org/wiki/Seemingly_unrelated_regressions

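### Table 3's minimum power of 84/81/77% is not the minimum of the closed-testing procedure: with the other two arms midway between the compared pair, power is about 76/73/68%

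*Protocol*

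**What the plan says.** Protocol 9.3 sets the sample size for the baseline-adjusted ANCOVA under the closed-testing procedure, "using a two-sided significance level of" 0.05. It claims at least 80% "power to detect a minimum effect size of 0.60 between any two treatment groups in either of the primary outcome measurements". Table 3, titled "Power for a sample size of 224 at end of study (56/treatment arm"), gives minimum power of 84%, 81% and 77% for adjusted effect sizes of 0.62, 0.60 and 0.57, at baseline correlations of 0.60, 0.57 and 0.50.

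Protocol 9.1 defines the procedure. On the first step: "If the overall test across the four groups is not significant, testing concludes and no treatment group is declared different from any other". On the last: "The final significance testing of any set of two treatment groups is only undertaken if the p-values for each of the two 3-intervention tests" containing that pair are both below 0.05. On the variance: "Each ANCOVA model will employ White's robust (information sandwich) estimate of the covariance matrix of the model coefficients as the basis for inference".

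Section 9.3 defines the effect size as the "absolute difference between any two groups divided by the standard deviation (SD"), whereas Table 3 labels it adjusted and lets it vary with the correlation. The later SAP replaces the ANCOVA on a single outcome with seemingly unrelated regression, which "allows a joint statistical test of both variables using a 2-DF chi-square test of the treatment arm difference in each model". It gives no new power figure.

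**The concern.** A pair must pass four tests, so its power cannot exceed that of the weakest. The first of these, the four-group test, depends on all four means. Two arms that differ by 0.60 are easier to separate when the other two sit at the ends than when they sit in between. Section 9.3 states no assumption about the other arms, yet it presents its figure as a minimum that holds for any pair.

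The unfavourable pattern is not far-fetched. All three active regimens contain metformin, so placebo at one end, one regimen at the other and two in between would be an ordinary result.

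What is at stake is how a null result is read. The trial is meant to show which approaches deserve larger studies. A reader who trusts 81% would read a non-significant pair as stronger evidence against a 0.60 difference than the design provides.

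**Working it through.** **Inputs.** 56 per arm, four equal arms, alpha 0.05 at each step, adjusted effects d = 0.62/0.60/0.57 (Protocol 9.1, 9.3 and Table 3). The residual SD is set to 1, because Table 3's effects already include the baseline correlation: d·√(1 − r²) is 0.496, 0.493 and 0.494 in the three rows.

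**Step 1: Table 3's own figures.** Put the compared arms at 0 and d and every other arm at d/2. The grand mean is d/2, so the noncentrality is 56 × (d²/4 + d²/4) = 56·d²/2, which is 10.76/10.08/9.10. A single three-group F test (2 and 168 − 4 = 164 df) with its third arm midway has power 83.7/81.1/76.7%. That rounds to Table 3 in all three rows. The protocol does not say the table was made this way; this is only an inference from the match.

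**Step 2: the four-group test in the same pattern.** The noncentrality is unchanged, but there are now 3 and 224 − 5 = 219 df. Power is 78.6/75.6/70.8%. Each value is below Table 3, so the full procedure cannot reach 84/81/77% here. This step needs no simulation.

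**Step 3: the full procedure.** Simulating all four tests jointly, each with its own error variance (400,000 trials per row), gives:

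| Position of the other two arms | d = 0.62 | d = 0.60 | d = 0.57 |
|---|---|---|---|
| Table 3 as stated | 84% | 81% | 77% |
| Both midway | 76% | 73% | 68% |
| All four means equally spaced | 78% | 75% | 70% |
| One midway, one at an end | 81% | 78% | 73% |
| One arm versus three equal arms | 86% | 83% | 78% |
| Two versus two | 86% | 83% | 79% |

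On a grid of positions at and between the compared pair, at d = 0.60, the lowest power is with both other arms midway (73%) and the highest is 83%. Positions tried outside the pair gave 80% or more.

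**Step 4: effect needed for 80% minimum power.** With both arms midway, d = 0.64 gives 79.4% and d = 0.645 gives 80.2%. So about 0.645 is needed at 56 per arm. Equivalently, d = 0.60 would need about 65 per arm (80.5%).

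**Step 5: sensitivity, both other arms midway.**
- White's robust (HC0) variance, patient-level ANCOVA, 12,000 trials per row: 77.3/74.1/68.8% with an F reference and 77.7/74.6/69.6% with a chi-square reference. A separate 8,000-trial check at 0.60 gave 75.2%.
- Table 3's effects look like 0.5/√(1 − r²) = 0.625/0.609/0.577 cut to two decimals. If so (an assumption), the minimum is 77.2/74.5/69.1%.
- If 0.60 were the unadjusted effect, the adjusted effect at r = 0.57 would be 0.60/√(1 − 0.57²) = 0.73. The four-group test would then have 91% power, but that reading does not reproduce Table 3.

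No variant reaches the stated figures as a minimum.

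**The case against.** The best defence is that the shortfall depends on the pattern of means. The main analysis compares each regimen with placebo, and the hypothesis is that at least one works. If one arm differs from three equal arms, if all active arms are equal, or if the arms split two and two, the full procedure has 83% or slightly more at 0.60. Minimum power could also be read as power at the minimum effect size. Both points have some force, but 9.3 claims the figure for any two groups under the full procedure and states no pattern, so its wording does not limit the claim to favourable cases.

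A second objection concerns where Table 3 came from. With the uncut effects, the three-group test gives 84.4/82.3/77.9%, which no longer rounds to Table 3, so the match depends on taking the two-decimal effects as exact. That is fair. The origin stays a conjecture, and the conclusion does not need it.

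Third, the shortfall at 0.60 is nearer 6–7 points than 8 under the robust variance that 9.1 prescribes. This is correct, and it is why the range is given.

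Finally, the trial is a proof of principle, and the SAP has since replaced the primary test, so a new table cannot alter the sample size. That limits the consequence to interpretation. It does not make the stated minimum correct.

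**Conclusion.** The concern holds. The figures of 84/81/77% are attainable in some patterns of means but are not the minimum of the procedure in 9.1. That minimum is about 76/73/68%, or about 77/74–75/69% with White's robust inference. At 0.60 the shortfall is 6 to 8 points, and the risk of missing a true difference in the worst pattern is about 27% (25–26% with robust inference) instead of 19%.

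This rests on 56 analysable patients per arm, Table 3's effects taken as baseline-adjusted, and the other arms lying at or between the compared pair. The first step of the argument, the four-group test's own power, rests on noncentral F alone. No test, estimate or type I error rate is affected. The mismatch in how the effect size is described is a minor wording point.

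**What to change.** Do one of two things in 9.3 and Table 3:

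- Replace the power column with the full-procedure minimum (about 76/73/68%), and give the adjusted effect detectable with 80% minimum power (about 0.645).
- Or state which pattern of the other arms is assumed (for example one arm against three equal arms, about 83% at 0.60) and show the minimum beside it.

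In either case, define the effect size in the text as baseline-adjusted so that it agrees with the table. Add one sentence saying that the stated power refers to the protocol's ANCOVA and does not carry over to the SAP's 2-DF joint test.

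The cost is a corrected sentence and table with a slightly less favourable figure. No extra patients are needed and no test changes.

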**Table 3: Power for a sample size of 224 at end of study (56/treatment arm)**

Minimum Power	Adjusted Effect Size	Correlation
84%	0.62	0.60
81%	0.60	0.57
77%	0.57	0.50

## ***9.4 Interim Analysis Plans***

The CoC will provide interim analyses of primary and major secondary trial outcomes to the DSMB on a predefined schedule. These results will not be shared with the study group unless the DSMB recommends early stopping of the trial.

## ***9.5 Stopping Rules***

The DSMB will monitor trial outcomes as they emerge for futility with specific rules outlined in the DSMB Monitoring Plan. This trial will not be stopped for lack of efficacy, as it is a proof-of-principle study with small numbers of participants in each treatment arm.

## ***9.6 Handling of Missing Data***

It is anticipated that a small number of participants will require immediate rescue therapy and be unable to have the 3-month post-washout evaluation. In these cases, the primary outcome will be missing. A sensitivity analysis which includes these participants will use a conservative approach by assuming that these participants have worse function than the participants who were measured. This is implemented by ranking the observed function values from the participants who completed the washout evaluation, and assigning a lower value (or worst rank) to those with missing data [89]. The groups are then compared using a Wilcoxon rank test.

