**CONFIDENTIAL**

### ***3.7 Randomization***

Randomization is stratified by clinical center and by prediabetes vs. diabetes status to ensure balance among the treatment groups with respect to anticipated differences in the participant populations. For each clinical center, the Coordinating Center (CoC) will generate two randomization schemes using a permuted block design. In this way, sample sizes across the four treatment arms will remain relatively equivalent as the trial progresses. The clinical center staff will use a computer-based system to input eligibility data and receive a random treatment assignment.

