## **7.4 Risk Management**

Glucose management (including study medications) will be provided free of charge to RISE Study participants while participating in the study. Participants will receive training about the proper use of hypoglycemic medications as well as education about the symptoms, causes and response to episodes of hyper- and hypoglycemia. Participants who develop symptomatic hypo- or hyperglycemia, or experience any side effects of medications or study procedures will be instructed to call the clinical site. The following procedures will be implemented to minimize risk to participants:

- *Hyperglycemia:* Participants will be instructed regarding the signs and symptoms of hyperglycemia and are to call the clinic with any concerns. To minimize the risk of symptomatic hyperglycemia, the following procedures will be followed:
  - If HbA1c >7% at any routine quarterly visit, therapy will be invigorated by frequent telephone contact and/or visits to encourage optimal medication adherence and lifestyle choices. HbA1c will be obtained at the next quarterly visit. If HbA1c remains >7% but  $\leq$ 8%, frequent contact will be maintained.
  - If HbA1c >8.0% at any routine quarterly visit, therapy will be invigorated and HbA1c will be repeated after 6 weeks. If it remains >8.0%, outcome assessment will be scheduled in 2 weeks (i.e., regardless of time since randomization).
  - If at any time – either a routine visit or when a participant is brought in due to symptoms – the HbA1c >9%, the HbA1c will be repeated within 2 weeks and, if confirmed, the participant will be scheduled for immediate outcome measurement.

- Metabolic decompensation: In the unlikely event that a study subject develops metabolic decompensation, defined as hyperglycemia (plasma glucose >300 mg/dl) accompanied by significant symptoms (e.g., vomiting, dehydration, lethargy) and/or moderate or large urinary ketones, the participant will be evaluated to determine if temporary use of insulin therapy is required. Once insulin is started, the site will attempt to wean insulin within 4 weeks. If insulin cannot be weaned off within 4 weeks, the patient will be censored at that time.
- If outcome measurements are performed prior to the scheduled time points of 12 or 15 months, once completed the participant will be referred back to their primary care provider for further care.

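### The worst-rank sensitivity analysis in Protocol 9.6 names no baseline covariate and no four-arm testing order, so a non-significant result after a significant primary would be ambiguous

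*Protocol*

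**What the plan says.** Protocol 9.6 expects a small number of participants to need rescue and miss the evaluation after the 3-month washout. Its sensitivity analysis ranks the observed post-washout values and places those with missing data below them. It ends: "The groups are then compared using a Wilcoxon rank test". It does not say whether baseline is used, which arms are compared, or in what order.

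Protocol 9.1 is explicit on all three for the primary: β-cell "function will be compared across the four treatment groups using an analysis of covariance model adjusted for baseline". A four-group test comes first, then three-group tests, then pairs. Protocol 9.3 powers that procedure: "A sample size of 56 per arm (224 total) at the end of the washout" is said to give at least 80% power for a "minimum effect size of 0.60 between any two treatment groups", with a baseline correlation of 0.57.

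The SAP replaces the single-outcome ANCOVA with two equations fitted jointly, one for log M/I and one for log C-peptide. Each is adjusted for its own baseline, and treatment is tested with a 2-DF chi-square. The SAP gives no missing-data or worst-rank method.

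Protocol 7.4 adds that if temporary insulin cannot be weaned within four weeks, "the patient will be censored at that time". It does not say what censoring means for a continuous Month 15 outcome.

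**The concern.** A sensitivity analysis for missing data should change one thing: the assumption about the missing values. Read naturally, 9.6 changes two, because it also drops the covariate on which the primary was powered. A plain Wilcoxon test can then turn non-significant simply because it is less precise. If that happens after a significant primary, the result does not show whether informative missingness or lost precision is responsible.

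The unstated testing order adds to this. With four arms and two co-primary outcomes, the comparisons made and the gates applied could be chosen after the data are seen.

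**Working it through.** **Inputs.** Protocol 9.3 and Table 3 give 56 per arm, two-sided α = 0.05, effect 0.60 and correlation r = 0.57. No rescue rate is given, so 0–10% per arm is assumed.

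**Reproducing Table 3.** Take two arms differing by 0.60 with a third at the midpoint. The noncentrality is 56 × 0.60² / 2 = 10.08. A three-group F test on 2 and 56 × 3 − 3 − 1 = 164 df has 81.1% power (stated: 81%). The other rows give 83.7% and 76.7% (stated: 84% and 77%).

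**Raw effect.** Table 3 labels its column "Adjusted Effect Size". A raw 0.50 SD divided by √(1 − r²) gives 0.625, 0.609 and 0.577 at r = 0.60, 0.57 and 0.50, close to the printed 0.62, 0.60 and 0.57. So 0.60 is read as an adjusted effect. The raw effect is 0.60 × √(1 − 0.57²) = 0.60 × 0.822 = 0.493. This is derived; the Protocol does not print it.

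**Pairwise power by formula,** Φ(d√(n/2) − 1.96) with n = 56 and √28 = 5.29:
- ANCOVA: d = 0.60 gives Φ(1.215) = 88.8%.
- Unadjusted t: d = 0.493 gives Φ(0.65) = 74.2%.
- Unadjusted Wilcoxon: d = 0.493 × √(3/π) = 0.482 gives Φ(0.59) = 72.2%.

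**Simulated pairwise power, worst ranks included (r = 0.57):**

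| Setting | Wilcoxon | Rank ANCOVA | Gain (points) |
|---|---|---|---|
| 56/arm, raw 0.493, no rescue | 70.2% | 84.7% | 14.5 |
| 56/arm, raw 0.50, no rescue | 72.5% | 86.4% | 13.9 |
| 60/arm, raw 0.493, no rescue | 74.3% | 87.6% | 13.3 |
| 60/arm, raw 0.493, lowest 5% in each arm | 71.7–72.1% | 86.1–86.4% | about 14 |
| 60/arm, raw 0.493, lowest 10% control, 5% treated | 74.2–74.4% | 87.6% | about 13 |

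If the worst-ranked participants are picked at random, the gain is 7–16 points. Rank ANCOVA was ahead in every setting tried, with type I error near 5%. With 3,000 or more runs per setting, the Monte Carlo standard error is about √(0.7 × 0.3 / 3000) = 0.8 points.

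**Wilcoxon against the Protocol's ANCOVA on completers** (56 per arm, raw effect about 0.5, rescue falling mainly on poor function):

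| Rescue | ANCOVA | Wilcoxon | Gap (points) |
|---|---|---|---|
| None (raw 0.50) | 88.6% | 72.5% | 16.1 |
| None (raw 0.493) | 87.4% | 70.2% | 17.2 |
| 5% in every arm | 86.3% | 66.9% | 19.4 |
| 5% control, 0% active | 82.1% | 73.3% | 8.8 |
| 10% control, 2% active | 78.8% | 75.0% | 3.8 |
| 2% control, 8% active | 91.6% | 61.2% | 30.4 |

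With no rescue and a raw effect of 0.50, the unadjusted t test has 74.7%. Of the 16.1-point gap, 88.6 − 74.7 = 13.9 come from dropping baseline and 74.7 − 72.5 = 2.2 from using ranks. Through every closed-testing step, with the other arms at the midpoint, power is 73.8% for ANCOVA and 51.0% for Kruskal–Wallis followed by Wilcoxon.

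**The case against.** - **The text is silent.** Section 9.6 says neither unadjusted nor two-sample. Both are the natural reading of a plain Wilcoxon test, but the exact criticism is that adjustment and comparisons are not specified. This stands.
- **A reader might infer that disagreement with the primary would be uninterpretable.** The documents do not support that. Agreement would be informative, the test is valid under randomization, and running the same Wilcoxon test on completers would help separate lost precision from the worst-rank assumption. Section 9.6 calls the analysis conservative and claims no power for it.
- **A reader might take 14 points as the shortfall against the primary.** It is the gap between Wilcoxon and rank ANCOVA. Against the Protocol's ANCOVA the gap is 16–17 points without rescue and about 4–30 with it. It is smallest when active treatment prevents rescue, a case this analysis exists to capture.
- **The primary has changed.** Under the SAP's joint test, pairwise power would be about 82–92% if only secretion changes, assuming a residual correlation between 0 and −0.5. More importantly, worse function has no single ranking for a two-variable outcome. A fix that does not name the ranked quantity would not repair the current plan.
- **Censored participants.** A reader might infer that 9.6 leaves them out because it opens with immediate rescue. Its implementing sentence covers anyone with missing data, so those without a Month 15 value are probably already included. A clarifying line is enough.
- **A reader might infer that 9.6 is the only analysis that keeps rescued participants.** Protocol 7.4 schedules early outcome measurement for confirmed high HbA1c, and section 9 calls for all available data. The documents do not say whether early values enter the primary.

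**Conclusion.** The concern holds as a gap in specification with a measurable cost in precision. As naturally read, 9.6 gives about 70–74% pairwise power where a baseline-adjusted rank analysis of the same scores gives about 85–88%. Across assumed rescue rates of 0–10% the gain is about 7–16 points. A significant primary followed by a non-significant worst-rank result would therefore be ambiguous.

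The figures assume that 0.60 is an adjusted effect and that r = 0.57 applies. The Protocol calls that correlation conservative, and the SAP says the power inputs came from studies using other methods. Correlations of 0.50 and 0.60 give ANCOVA-to-Wilcoxon losses of about 13 and 18 points without rescue. The rescue rates are assumptions. The change is worth making, but the validity of the primary analysis does not depend on it.

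**What to change.** Replace the last sentence of 9.6 with: 'Worst-rank scores are regressed on treatment and the rank of the baseline value (rank ANCOVA), using the four-group, three-group and pairwise gates of 9.1.'

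In the SAP, name what is ranked: each C-peptide response (steady state and maximal) with its own baseline and, if wanted, log M/I separately.

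Add one line saying that participants censored under 7.4 with no Month 15 value belong to the worst-rank set.

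The plain Wilcoxon test can stay as a supporting analysis. The cost is SAP wording, a modest amount of code and slightly more output. No new data are needed, because the baseline clamp is done before randomization.
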